2.4.5.8 Analyses of ophthalmological examination variables

Number and percentages of patients with any abnormal ophthalmological examination on any eye at any time (whether present at screening or not) as well as number and percentages of patients with any new onset of abnormal ophthalmological examination on any eye during the TEAE period (see [Section 2.1.4](#)) as per investigator (site ophthalmologist) assessment will be summarized. A listing will be provided for patients with new onset of abnormal ophthalmological examination on any eye during the TEAE period.

Number and percentages of patients with any definite worsening of lens opacity on any eye as well as number and percentages of patients with any possible worsening of lens opacity on any eye during the TEAE period (see [Section 2.1.4](#)) as per central reader assessment will be summarized along with a description of lens opacity grading according to the ARLNS grading system (1). A listing will be provided for patients with worsening (definite or possible) of lens opacity on any eye during the TEAE period.

2.4.5.9 Analyses of depression data

Descriptive statistics for values and changes from baseline in BDI-II total score will be presented by treatment arm for each time point during the on-treatment period (see [Section 2.1.4](#)). All measurements will be assigned to analysis windows defined in [Section 2.5.4, Table 3](#) in order to provide an assessment for Week 2 to Week 52 time points. BDI-II total score continuous data will be summarized using the number of available data, mean, standard deviation (SD), median, minimum and maximum for each treatment arm.

In addition, the worst (highest) BDI-II total score value during the treatment-emergent period will be categorized and summarized using the number and percentage of patients in each treatment arm within each of the following categories:

- 0-13 (minimal depression)
- 14-19 (mild depression)
- 20-28 (moderate depression)
- 29-63 (severe depression)

In addition, the worst (highest) score during the treatment-emergent period for suicidal thoughts (item 9 of BDI-II) will be summarized using the number and percentage of patients in each treatment arm within each of the following categories:

- I don't have any thoughts of killing myself
- I have thoughts of killing myself but I would not carry them out
- I would like to kill myself
- I would kill myself if I had the chance

In addition, the number of participants with BDI-II worsening from baseline during the treatment emergent period will be summarized.

2.4.6 Analyses of pharmacokinetic and pharmacodynamic variables

Pharmacokinetic and pharmacodynamic variables will be presented for the Pharmacokinetics and pharmacodynamic populations respectively (see [Section 2.3.3](#) and [Section 2.3.4](#)), separately for Part 1 and Part 2 of the study. In Part 1, data will be presented separately for Japanese and non-Japanese patients.

2.4.6.1 Analyses of pharmacodynamic variables

Pharmacodynamic data will be described separately for Part 1 and Part 2 of the study, and separately for Japanese and non-Japanese patients. Data of patients from Part 1 who are rerandomized in Part 2 will not be included in Part 2 and will be presented separately.

Part 1: Dose escalation phase

For all pharmacodynamics parameters, raw data and percent change from baseline will be summarized in descriptive statistics by treatment group and scheduled time of measurement for each population separately (Japanese and non-Japanese patients). No formal statistical comparison will be made.

Additionally, graphs over time will be presented plotting mean +/- SD by treatment group for each population separately (Japanese and non-Japanese patients).

Part 2: Treatment phase

In Part 2, pharmacodynamics data will be presented separately for the two following periods:

- Analysis of the 52-week blinded treatment period of Part 2. This analysis will present pharmacodynamics data from baseline to 52 weeks. Pharmacodynamic analyses will compare the two treatment arms:
 - Placebo
 - GZ/SAR402671 15mg
- Analysis of the 156-week treatment period. This analysis will present all pharmacodynamics data from baseline to 156 weeks, combining the 52-week blinded treatment period and the 104-week long-term follow-up period. Pharmacodynamic analyses will compare the two treatment strategies:
 - Delayed start: patients randomized to receive placebo for 52 weeks, then GZ/SAR402671 15mg for 104 weeks.
 - Early start: patients randomized to receive GZ/SAR402671 15mg for 52 weeks, then continued GZ/SAR402671 15mg for 104 weeks.

Percent change from baseline to Week 26 and Week 52 in plasma GL-1 will be analyzed using a MMRM including data available at Week 2, Week 4, Week 13, Week 26, Week 39 and Week 52 analysis time windows (as defined in Table 6). The model will include the fixed categorical effects of treatment group (GZ/SAR402671 versus placebo), randomization strata (use of levodopa/PD medication: yes/no, MoCA score <26: yes/no and severe GBA mutation: yes/no), time point (as defined in Table 6), treatment-by-time point interaction, randomization strata-by-time point interaction as well as the continuous fixed covariates of baseline and the baseline-by-time point interaction

Percent change from baseline to Week 52 in CSF GL-1 will be analyzed using an Analysis of Covariance (ANCOVA). The model will include the fixed categorical effects of treatment group (GZ/SAR402671 versus placebo), randomization strata (use of levodopa/PD medication: yes/no, MoCA score <26: yes/no and severe GBA mutation: yes/no), as well as the continuous fixed covariate of baseline.

For all other continuous exploratory endpoints, descriptive statistics by visit will be provided for each treatment arm. Summary statistics (including number of available data, mean, SD, median, minimum and maximum) will be presented for value, change from baseline and percent change

from baseline (when applicable). Further analyses using MMRM (if repeated assessments) or ANCOVA (if single assessment) may be performed when appropriate.

2.4.6.2 Analyses of pharmacokinetic variables

Pharmacokinetic data will be described separately for Part 1 and Part 2 of the study, Data of patients from Part 1 who are rerandomized in Part 2 will not be included in Part 2.

For Part-1 Dose escalation phase: Pharmacokinetic parameters of GZ/SAR402671 in plasma and in CSF will be summarized by descriptive statistics (such as mean, geometric mean, median, SD, SEM, CV, minimum, and maximum) by visit and treatment groups. Descriptive statistics could be provided by specific subgroups (e.g Japanese and non-Japanese), as needed. PK samples collected outside of the sampling time window as mentioned in section 2.1.5 (Pharmacokinetic variables) or PK samples collected as unscheduled samples will be classified as “undefined concentrations”. No descriptive statistics will be performed on these concentrations. This analysis will be performed under the responsibility of Pharmacokinetics, Dynamics and Metabolism (PKDM), Bridgewater, Sanofi.

For Part-2 Treatment phase: Pharmacokinetic parameters of GZ/SAR402671 in plasma and in CSF will be summarized by descriptive statistics (such as mean, geometric mean, median, SD, SEM, CV, minimum, and maximum) by visit. Descriptive statistics could be provided by specific subgroups (e.g Japanese and non-Japanese), as needed. PK samples collected outside of the sampling time window as mentioned in section 2.1.5 (Pharmacokinetic variables) or PK samples collected as unscheduled samples will be classified as “undefined concentrations”. No descriptive statistics will be performed on these concentrations. This analysis will be performed under the responsibility of Pharmacokinetics, Dynamics and Metabolism (PKDM), Bridgewater, Sanofi.

Other statistical analyses described below will be performed under the responsibility of Biostatistics, Sanofi.

Part 1: Dose escalation phase

Accumulation

For C_{\max} and AUC_{0-24} , accumulation will be assessed with a linear model for each population separately (Japanese and non-Japanese patients),

$$\text{Log(Ratio of Week 4 versus Day 1)} = \text{Dose} + \text{Error}$$

with dose as fixed effect using SAS Proc Mixed®.

Accumulation ratio of Week 4 versus Day 1 will be assessed for each population separately (Japanese and non-Japanese patients) and for each dose level separately as well as pooled across dose levels within the model framework. Estimate and 90% confidence interval for the accumulation ratio will be obtained by computing estimate and 90% confidence interval for the logarithm of the accumulation ratio within the linear model framework, and then converting to the accumulation ratio by the antilog transformation.

Listings of individual accumulation ratios will be provided, along with their descriptive statistics.

Dose proportionality

For each population separately (Japanese and non-Japanese patients) and for C_{max} , AUC_{0-24} and CSF concentration (on Week 4 only), dose proportionality will be assessed on Day 1 and Week 4 separately using the empirical power model (pharmacokinetics parameter = $\alpha \times \text{dose}^\beta$), along with an “estimation” interpretation, according to the recommendations in Gough et al. (1995):

“The empirical power model provides a readily and interpretable measure of the degree of non-proportionality, which can be used both to confirm proportionality and to assess the pharmacokinetic and clinical significance of any departures.”

“The analysis of dose proportionality studies, however, requires estimation rather than significance testing in order that the pharmacokinetic and clinical significance of any non-proportionality can be assessed.”

The power model will be fit on the log-transformed scale: $\log(\text{parameter}) = \log(\alpha) + \beta \times \log(\text{dose})$. Model lack-of-fit will be assessed by residual plots, and by an F-test of the residual mean square versus the pure error residual mean square. If the model fit is adequate, estimates with 90% confidence intervals for β will be obtained, and further used to obtain estimates and 90% confidence intervals for the pharmacokinetics parameter increase associated with an r-fold ($r = 2$ and $r = \text{high dose} / \text{low dose}$) increase in dose, by exponentiating r to the powers of the β estimate and confidence limits,

$$r^{b \pm t \times SE(b)}$$

If there is evidence of model lack-of-fit, then attempts could be made to fit the model over a reduced dose range (eg, exclude 1 extreme dose level). Otherwise, a linear model will be used, with fixed term for dose, using logarithms of the relevant pharmacokinetics parameters. Estimates with 90% confidence intervals for the parameter increases associated with pairwise dose increases will be obtained by first computing estimates with confidence intervals for differences between pairwise dose groups in the linear model framework, and then converting to ratios using the antilog transformation.

Dose effect

The distribution of t_{max} values will be represented by histogram plots for each dose level.

Variance components

For each population separately (Japanese and non-Japanese patients), within-subject and total standard deviations for $\log(C_{max})$ and $\log(AUC_{0-24})$ will be estimated by equating observed and expected means squares within the following linear model framework,

$$\log(\text{parameter}) = \text{Dose} + \text{Day} + \text{Day} \times \text{Dose} + \text{Subject}(\text{Dose})$$

with fixed effects for dose, day and day-by-dose interaction, and with subject-within-dose as random effect. 90% confidence intervals will be computed using the simple χ^2 method for the within-subject SD, and the Graybill-Wang procedure for the total SD.

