1.1 STUDY DESIGN AND RANDOMIZATION

This is a two-part, multicenter, multiple-country, randomized, double-blinded, placebo-controlled study in early-stage Parkinson Disease (PD) patients carrying a GBA mutation. The study will be divided into 2 consecutive parts. Part 1 will be a randomized, double-blinded, placebo-controlled dose escalation study, utilizing a sequential cohort design. Part 1 will allow selection of the dose of GZ/SAR402671 for Part 2, a randomized, double-blind, placebo-controlled, 2-arm study of the efficacy and safety of GZ/SAR402671. Part 1 will be conducted only in selected sites (approximately 20 sites [including 4 Japanese sites]); Part 2 will be conducted at multiple sites (approximately 50). Part 2 will start after the appropriate dose for Part 2 is selected in Part 1.

In Part 1, during the screening/baseline period, from Day -60 to Day -1, patients will provide informed consent and undergo screening assessments to determine trial eligibility and undergo baseline measurements. If all eligibility criteria are met, patients will enter the trial. Part 1 will determine the safety and tolerability of GZ/SAR402671 at 4, 8, and 15 mg in early-stage PD patients carrying a GBA mutation by using a dose escalation scheme (4 weeks to assess safety and tolerability of dose and a minimum of an additional 4 weeks to further assess safety and tolerability and any potential changes in other exploratory endpoints in each dose cohort). There will be 3 sequential cohorts that will be placebo-controlled:

- Cohort 1: 4 patients (or 3 patients in Japan) on GZ/SAR402671 4 mg and 1 patient on placebo
- Cohort 2: 4 patients (or 3 patients in Japan) on GZ/SAR402671 8 mg and 1 patient on placebo

- Cohort 3: 4 patients (or 3 patients in Japan) on GZ/SAR402671 15 mg and 1 patient on placebo

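### The lack-of-fit F-test for the Part 1 dose-proportionality power model, read literally, puts pure error in both numerator and denominator, so it is severely conservative and tilts reporting towards a single slope

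*SAP*

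**What the plan says.** The dose-proportionality part of SAP section 2.4.6.2 fits a power model to Cmax, AUC0-24 and, at Week 4 only, CSF concentration. Japanese and non-Japanese patients are analysed separately, and "dose proportionality will be assessed on Day 1 and Week 4 separately using the empirical power model". The model is a straight line in log dose: "The power model will be fit on the log-transformed scale".

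On adequacy, the SAP relies on residual plots together with a formal check "by an F-test of the residual mean square versus the pure error residual mean square". It gives no ratio, degrees of freedom, significance level or critical value.

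What follows depends on the answer. "If the model fit is adequate, estimates with 90% confidence intervals for β will be obtained", and these are turned into the increase expected for an r-fold rise in dose. If there is evidence of lack of fit, "attempts could be made to fit the model over a reduced dose range (eg, exclude 1 extreme dose level"); failing that, dose is fitted as a factor on the log scale and pairwise dose ratios are given with 90% intervals.

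**The concern.** A lack-of-fit test splits the residual sum of squares into lack of fit and pure error, and compares the mean squares of those two independent pieces. The SAP names the whole residual mean square as the quantity set against pure error. Pure error is then in both parts of the ratio, which cannot be referred to an F table. With three doses and a straight line, only 1 of the residual degrees of freedom carries information on misfit, so the signal is diluted by pure error.

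At stake is which model-based result is reported. A conservative test favours the single slope, and a departure at one dose is then averaged into it without the pairwise ratios and intervals that would show it.

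**Working it through.** The plan states no figure for this test, so there is none to reproduce.

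**Inputs from the SAP**
- Three doses: 4, 8 and 15 mg (section 1.1).
- A line with two parameters (section 2.4.6.2).
- Planned active patients: 12 non-Japanese, 4 per dose, and 9 Japanese, 3 per dose (sections 1.1 and 1.3.1).
- Each day is fitted separately, so each patient gives one value per fit.

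**Assumptions, because the SAP is silent**
- Alpha 0.05.
- Log-scale SD 0.2 to 0.4, with 0.3 as the central value.
- Full cohorts.
- The literal ratio is referred to F(n − 2, n − 3).

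**Step 1: the ratio.** SS_res = SS_LOF + SS_PE, with degrees of freedom n − 2 = 1 + (n − 3). The standard statistic is F_LOF = SS_LOF / [SS_PE/(n − 3)], distributed F(1, n − 3) when the line fits. The literal ratio is

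R = [SS_res/(n − 2)] / [SS_PE/(n − 3)] = [(n − 3) + F_LOF] / (n − 2).

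- n = 12: R = (9 + F_LOF)/10, never below 0.90.
- n = 9: R = (6 + F_LOF)/7, never below 0.857.

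A variable with such a floor is not an F variable.

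**Step 2: the effective threshold.** R exceeds its critical value only if F_LOF > (n − 2) × F_crit − (n − 3).

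| | n = 12 | n = 9 |
|---|---|---|
| Critical value used for R | F(10,9) = 3.137 | F(7,6) = 4.207 |
| F_LOF needed | 10 × 3.137 − 9 = 22.37 | 7 × 4.207 − 6 = 23.45 |
| Correct cut-off for F_LOF | F(1,9) = 5.12 | F(1,6) = 5.99 |
| Actual size at nominal 5% | 0.11% | 0.29% |
| Actual size at nominal 10% | 0.37% | 0.81% |

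Simulation of 400,000 data sets gave sizes of 0.11% and 0.28% at nominal 5%.

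**Step 3: power.** Let the 15 mg geometric mean lie off the line through 4 and 8 mg by a given fold. With m patients per dose, the noncentrality is λ = m × c × (ln fold)² / SD².

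The contrast for departure from linearity in log dose is (0.629, −1.322, 0.693), whose squares sum to 2.623. So c = 0.693²/2.623 = 0.183. For two-fold, SD 0.3 and m = 4, λ = 4 × 0.183 × 0.480/0.09 = 3.91. Power is the noncentral F(1, n − 3) probability of exceeding each cut-off.

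| Departure at 15 mg | SD | n | Standard test | Literal test |
|---|---|---|---|---|
| 2-fold | 0.2 | 12 | 75% | 13.5% |
| 2-fold | 0.3 | 12 | 42% | 4% |
| 2-fold | 0.4 | 12 | 26% | 1.5% |
| 2-fold | 0.3 | 9 | 30% | 4% |
| 3-fold | 0.2 | 12 | 99% | 53% |
| 3-fold | 0.3 | 12 | 80% | 16% |
| 3-fold | 0.3 | 9 | 62% | 13% |
| 4-fold | 0.2 | 12 | nearly 100% | 82% |

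**Step 4: the reduced-range refit.** Dropping one of three doses leaves two doses and two parameters, so lack of fit has 2 − 2 = 0 df. The refitted line passes through both dose means and cannot show misfit.

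**The case against.** The strongest reply is that the sentence is loose shorthand for the standard test. It appears under lack of fit, and isolating pure error is the defining step of that test. The F(10,9) and F(7,6) references are also this review's reading, since the SAP gives none. That is fair: the document does not settle what will be programmed. But the one quantity it does name for comparison with pure error is the wrong one, and a programmer following it literally would produce an invalid test.

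Several stronger readings are tempting and are not supported.

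- **That the F-test alone decides which model is reported.** Residual plots are used with it, and the trigger is evidence of lack of fit, not a p-value. The plots have no stated criterion and show only 3 or 4 patients per dose, so they are a partial safeguard.
- **That the literal test never finds misfit.** It finds 53% of three-fold and 82% of four-fold departures at SD 0.2 with 12 patients. Some of the insensitivity comes from cohort size: at SD 0.3 even the standard test misses a two-fold departure more often than not.
- **That a departure at the top dose would be hidden.** Section 2.4.6.2 separately summarises Part 1 PK by visit and treatment group, including geometric means and CVs. Only the model-based ratios and intervals may go unreported.
- **That dose selection or Part 2 is affected.** The review that selects the dose uses descriptive statistics only (section 3.2), and no Part 2 endpoint or alpha depends on this model.
- **That the reduced-range refit has to go.** It is optional, and with two doses the slope is simply their ratio re-expressed. It just cannot be cited as evidence of adequate fit.

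**Conclusion.** The point stands as a modest correction. The rule as written yields a ratio that is not F-distributed, with an actual size near 0.1% (12 patients) or 0.3% (9 patients) at an assumed alpha of 0.05. For a two-fold departure at 15 mg with 12 patients, its power is 1.5% to 13.5% over log-SD 0.2 to 0.4, against 26% to 75% for the standard test. The size results rest on the assumed alpha, the literal reading and full cohorts; the power results also rest on the assumed SD.

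The consequence is a tilt towards reporting one slope without pairwise ratios. That sits awkwardly with the section's own stated preference for estimation over testing. It is confined to the supportive Part 1 PK analysis.

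**What to change.** Replace the F-test wording in section 2.4.6.2 with: lack of fit will be tested by F = lack-of-fit mean square (residual SS minus pure-error SS, df = number of doses − 2 = 1) divided by the pure-error mean square (df = n − 3, that is 9 non-Japanese and 6 Japanese at planned size), at a stated alpha.

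Report the dose-as-factor pairwise ratios with 90% confidence intervals alongside the power-model slope whatever the test shows, because even the standard test is weak at these sizes. Add that a refit on two remaining doses is saturated and is not evidence of fit; deleting that option is not essential.

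If the Part 1 PK output has already been produced, check which ratio was programmed and add the pairwise table. The cost is one sentence of wording and one extra table per parameter, from a model the SAP already specifies.

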2.4.7 Analyses of quality of life variables

Part 1: Dose escalation phase

Descriptive statistics for values and changes from baseline will be presented by treatment arm for each time point. Continuous data will be summarized using the number of available data, mean, standard deviation (SD), median, minimum and maximum for each treatment arm.

Summary statistics will be provided for the following exploratory endpoints:

- PDQ-39 questionnaire, including:
 - Mobility
 - Activities of daily living
 - Emotional well-being
 - Stigma
 - Social support
 - Cognition
 - Communication
 - Bodily discomfort
 - PDQ-39 single index (PDQ-39-SI)
- EQ5D: utility index and overall health status
- HRPQ including:
 - Hours of lost work due to absenteeism in (a) workplace and (b) household
 - Hours of lost work due to presenteeism in (a) workplace and (b) household
 - Total [absenteeism + presenteeism] hours of lost work in (a) workplace and (b) household
 - % of scheduled work lost due to absenteeism, presenteeism, and total productivity loss in (a) workplace and (b) household

Part 2: Treatment phase

Data of patients from Part 1 who are rerandomized in Part 2 will not be included in Part 2 and will be presented separately.

Quality of life endpoints described in [Section 2.1.3.3](#) will be analyzed using descriptive statistics for values and changes from baseline will be presented by treatment arm for each time point. Continuous data will be summarized using the number of available data, mean, standard deviation (SD), median, minimum and maximum for each treatment arm.

2.5 DATA HANDLING CONVENTIONS

2.5.1 General conventions

The following formulas will be used for computation of parameters.

Demographic formulas

- $$\text{BMI} = \frac{\text{weight(kg)}}{\text{height(m)}^2}$$

Parkinson's disease history

- Time since onset of symptoms (in years):
 - If complete date of onset of symptoms available: (date of informed consent - date of onset of symptoms)/365.25
 - If only year and month of onset of symptoms available: (year/month part of date of informed consent - year/month part of date of onset of symptoms)/12
 - If only year of onset of symptoms available: (year part of date of informed consent - year part of date of onset of symptoms)
- Time since diagnosis (in years)
 - If complete date of diagnosis available: (date of informed consent - date of diagnosis)/365.25
 - If only year and month of diagnosis available: (year/month part of date of informed consent - year/month part of date of diagnosis)/12
 - If only year of diagnosis available: (year part of date of informed consent - year part of date of diagnosis)

ECG formulas

- Bazett (QTcB (eçums)):
$$\text{QT (ms)} / \sqrt{60 / \text{HR (bpm)}}$$
- Fridericia (QTcF (ms)):
$$\text{QT (ms)} / \sqrt[3]{60 / \text{HR (bpm)}}$$

Renal function formulas

eGFR value will be derived using the CKD-EPI formula (6):

$$\text{eGFR (mL/min/1.73m}^2\text{)} = 141 \times \min(\text{Scr}/\kappa, 1)^\alpha \times \max(\text{Scr}/\kappa, 1)^{-1.209} \times 0.993^{\text{Age}} \times 1.018 \text{ [if female]} \times 1.159 \text{ [if black]}$$

where:

- Scr is serum creatinine in mg/dL (serum creatinine in $\mu\text{mol/L}$ should be divided by 88.4)
- κ is 0.7 for females and 0.9 for males
- α is -0.329 for females and -0.411 for males
- min indicates the minimum of Scr/κ or 1
- max indicates the maximum of Scr/κ or 1
- For calculation of eGFR in Asian population of patients (except Japanese patients), the Asian-modified CKD-EPI (aCKD-EPI) equation will be used (7):
 - Female and $\text{SCr} \leq 0.7$: $151 \times (\text{SCr} / 0.7)^{-0.328} \times (0.993)^{\text{Age}}$
 - Female and $\text{SCr} > 0.7$: $151 \times (\text{SCr} / 0.7)^{-1.210} \times (0.993)^{\text{Age}}$
 - Male and $\text{SCr} \leq 0.9$: $149 \times (\text{SCr} / 0.9)^{-0.412} \times (0.993)^{\text{Age}}$
 - Male and $\text{SCr} > 0.9$: $149 \times (\text{SCr} / 0.9)^{-1.210} \times (0.993)^{\text{Age}}$
- For calculation of eGFR in Japanese patients, CKD-EPI Study equation multiplied by a Japanese coefficient of 0.813 will be used (8).

